5.11 Duration of T1DM

Duration of T1DM is defined as:

Duration of T1DM (in years) = (Date of ICF signed – date of diagnosis +1)/365.25.

Incomplete T1DM diagnosis date will be imputed as follows:

- If only year available, impute as 01-Jul of the year;
- If year and month are available, impute as 15th of the month.

For subjects with missing T1DM diagnosis date, the duration of T1DM will set to be missing.

5.12 Cohorts

There are three age cohorts in the study: Cohort 1(13 to 17 years), Cohort 2 (8 to 12 years) and Cohort 3 (4 to 7 years). Data will be summarized based on the cohort the subject enrolled into.

6 ANALYSIS POPULATION

6.1 Safety

All subjects in the study who receive a dose of AFREZZA[®] will be included in the safety population.

All analyses, except for PK analyses will be performed on the Safety Population.

6.2 PK (Pharmacokinetic)

All subjects without any major deviations related to study drug administration (no sneezing or coughing right after AFREZZA[®] inhalation on Day 1), and for whom any PK parameters are available, will be included in the PK population.

All PK analyses will be performed on the PK Population.

7 INTERIM ANALYSES

Interim analyses (IA) will be conducted on a cohort by cohort basis upon the completion of each cohort's PK and 4-week Titration Phase of this protocol. Tables/listings/figures produced for the IA will be a subset of those produced for the final analysis. The same analysis methods will be used, with the exception that only data collected in the titration phase will be included.

Tables/listings/figures to be included in the interim analyses are indicated in Appendix 3.

Pharmacokinetics and safety data will be reviewed on a rolling basis by the Sponsor and the DMC in order to allow enrollment in Cohorts 2 and 3. Tables/listings/figures to be included in the DMC package are indicated in Appendix 3.

8 STATISTICAL METHODS

8.1 General Considerations

In this study, unless otherwise specified, all analyses will be performed in a descriptive manner by age cohort (including ‘Cohort 1’, ‘Cohort 2’, ‘Cohort 3’ and ‘Total’). The ‘Total’ group will include all subjects in the analysis population.

Where appropriate, all dimensions will be summarized in metric units, but listings will, in addition, represent values as collected.

For continuous variables, the number of subjects, mean, standard deviation, median, minimum, and maximum values will be displayed, as appropriate according to the type of data. The minimum and maximum will be displayed to the same number of decimal places that the data were recorded to. The mean and median will have 1 extra decimal place and the standard deviation will have 2 extra decimal places. The geometric mean and coefficient of variation (CV) will have 2 extra decimal places. Confidence interval (of the mean) will have the same decimal precisions as the mean.

For categorical variables, frequency counts and percentages of total for each category will be presented; missing values will be treated as a separate category, where appropriate. Percentage will be presented in 1 decimal place.

Visit specific data (e.g., 7-point SMBG or pulmonary function tests) will be summarized by analysis visit, which is defined based on the visit windows specified in Section 0

Non-visit specific data (e.g., hypoglycemic events or daily dose) will be summarized by study period and/or by time interval. See relevant sections for more details.

8.1.1 **Data Handling/Imputation Methods**

8.1.1.1 **Missing Data Imputation**

Unless otherwise specified, missing data other than start date of adverse events (AE) or start/end date of concomitant medications (CM) will not be imputed.

The imputation rules for start date of Aes and start/end date of CMs are as follows:

Adverse Events

- Start date
 - If the start date is completely missing, the start date is set to the date of first dose.
 - If the year is present and the month and day are missing or the year and day are present and the month is missing:

If year = year of first dose, then set month and day to month and day of first dose

Version Date: 17-Jan-2020

- If year < year of first dose, then set month and day to December 31.
- If year > year of first dose, then set month and day to January 1st.
- If the month and year are present and the day is missing:
 - If year = year of first dose and
 - If month = month of first dose then set day to day of first dose date
 - If month < month of first dose then set day to last day of month
 - If month > month of first dose then set day to 1st day of month
 - If year < year of first dose then set day to last day of month
 - If year > year of first dose then set day to 1st day of month
- For all other cases, set the start date to the date of first dose

Concomitant Medications

- Start date
 - If the start date is completely missing, then the start date will not be imputed.
 - If the year is present and the month and day are missing or the year and day are present and the month is missing:
 - Set month and day to January 1st.
 - If the year and month are present and the day is missing:
 - Set day to 1st day of month.
- End date
 - If the end date is completely missing, then the end date will not be imputed.
 - If the year is present and the month and day are missing or the year and day are present and the month is missing:
 - Set month and day to December 31.
 - If the year and month are present and the day is missing:
 - Set day to last day of the month.

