10.2.5 Cough

Cough as an isolated symptom will be reported as an AE in the e-CRF. For cough associated with a defined clinical entity (e.g., upper respiratory tract infection), the appropriate diagnosis associated with the cough will be recorded in the AE e-CRF.

10.3 OBLIGATION OF THE INVESTIGATOR REGARDING SAFETY REPORTING**10.3.1 General guidelines for reporting adverse events**

All AEs, regardless of seriousness or relationship to IMP/NIMP, occurring between consent/assent and the end of the study will be recorded.

AEs are to be recorded as defined by the protocol on the corresponding e-CRF for subjects who are enrolled and for those who fail screening.

For screen failed subjects, recording in the e-CRF is only performed in case of an SAE occurring during the screening period or in case of an AE when some study-specific screening procedures expose the subject to safety risks. Whenever possible, diagnosis or syndrome should be reported instead of individual associated symptoms (e.g., record “Influenza” not fever, chills, etc). The Investigator should specify the date of onset, intensity (see definitions in Section 10.2.1), action taken with respect to IMP/NIMP, corrective treatment/therapy given, additional investigations performed, outcome, and Investigator’s opinion as to whether there is a reasonable possibility that the AE was caused by the IMP/NIMP.

In order to ensure the safety of the subjects, the Investigator should take appropriate measures to follow all AEs until clinical recovery is complete and laboratory results have returned to normal, or until no further improvement is expected, or until death. Follow-up of the AE resolution/status will end at the follow-up visit. If necessary, SAEs will be followed beyond the last planned visit per protocol until resolution, no further improvement is expected, or death. Additional investigations of the SAE may be requested by the Sponsor.

When treatment is prematurely discontinued, an early termination (ET) visit should be conducted as soon as possible. Laboratory, vital sign, or electrocardiogram abnormalities are to be recorded as AEs only if:

- Laboratory and/or vital signs not specifically addressed elsewhere in the protocol change $\geq 10 \times$ the upper or the lower limits of normal and are undesired, and are a change from the pre-enrollment assessment values, and/or
- Are symptomatic, and/or

- Are clinically significant

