8.3 Safety Analyses

8.3.1 Adverse Event

Definition

Adverse Event (AE)

An AE is any untoward medical occurrence in a subject administered a pharmaceutical product and which does not necessarily have to have a causal relationship with this treatment. An AE can be any unfavorable and unintended sign (e.g., an abnormal laboratory finding), symptom, or disease temporally associated with the use of a drug, and does not imply any judgment about causality.

General

All adverse events will be described with cohort, start date, resolution date, seriousness, severity (mild, moderate, severe), outcome of AE (recovered/resolved, recovering/ resolving, recovered/resolved with sequelae, not recovered/resolved, death related to AE, and unknown), relationship to study treatment (definite, probable, possible, unlikely, and not related), action taken with investigational medicinal product (dose increased dose, dose not changed, dose reduced, dose interrupted, dose withdrawn, not applicable, and unknown), other action taken (treatment given and withdrawn from the trial).

Coding

Adverse events will be coded by the system organ class and preferred terms specified in the MedDRA (version 20.1) dictionary.

Classification

Prior Adverse Event

A prior adverse event is defined as adverse event whose start date is before the date of the first dose of study drug.

A subject listing will be presented for all the prior adverse events.

Treatment-Emergent Adverse Event (TEAE)

An adverse event is treatment-emergent if the start date is on or between the date of the first dose of study drug and the date of the last dose of study drug plus 30 days (inclusive). Worsening of a pre-treatment event during the trial is also treatment emergent.

Follow-up Adverse Event

A follow-up adverse event is defined as adverse event whose start date is between the date of the last dose of study drug plus 30 days (exclusive) and the date of the last visit day of the follow-up period.

A subject listing will be presented for all the follow-up adverse events.

Special Adverse Event

The following special treatment-emergent adverse event will be identified and reported from the adverse event database.

- Acute bronchospasm
- Verified clinically relevant decline in pulmonary function
- Hypersensitivity reactions, including anaphylaxis, which can occur with insulin products, including AFREZZA
- Diabetic ketoacidosis

Serious Adverse Event

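### The SAP's rule for incomplete adverse event start dates ignores the recorded end date, so a screening event that ended before dosing can be tabulated as treatment-emergent with a start after its end

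*SAP*

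**What the plan says.** SAP 8.1.1.1 (Missing Data Imputation, Adverse Events) sends an incomplete start date to the first-dose date in four situations:

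- nothing is known: "If the start date is completely missing, the start date is set to the date of first dose";
- the year is known but not the month: "If year = year of first dose, then set month and day to month and day of first dose";
- the month and year are known, the year is that of first dose, and the day is missing: "If month = month of first dose then set day to day of first dose date";
- anything left over: "For all other cases, set the start date to the date of first dose".

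Each rule compares the partial start date with the first-dose date and nothing else. The same section limits imputation: "missing data other than start date of adverse events (AE) or start/end date of concomitant medications (CM) will not be imputed". An adverse event end date in the analysis data is therefore a recorded value. SAP 8.3.1 confirms that it is collected: "All adverse events will be described with cohort, start date, resolution date, seriousness".

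Classification in SAP 8.3.1 rests on the start date. "A prior adverse event is defined as adverse event whose start date is before the date of the first dose of study drug". An event is treatment-emergent when it starts from the first-dose date up to 30 days after the last dose; worsening of a pre-treatment event also counts. Events are collected before dosing: under Protocol 10.3.1, all those "occurring between consent/assent and the end of the study will be recorded", and Protocol 12.1 gives a screening period of 7 to 21 days.

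**The concern.** Moving an unknown start to the first-dose date is a sound conservative default when the event might have begun on treatment. It is wrong when the record shows that the event was over before the first dose, because the timing is then not in doubt. The rule still produces a treatment-emergent event, with an onset later than its resolution. No other section of the SAP or protocol overrides this, and the worsening clause does not rescue it, since an event that has already resolved cannot worsen on treatment.

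Such an event would enter the treatment-emergent tables and drop out of the prior-event listing (Listing 16.2.7.3). The treatment-emergent table by system organ class and preferred term and the matching listing are in the DMC package (SAP Appendix 3). Events of special interest are taken from treatment-emergent events (SAP 8.3.1), and the cough profile counts cough between first and last dose dates (SAP 8.3.4). A respiratory event that ended before any inhalation could therefore be shown as on-treatment for an inhaled product.

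**Working it through.** The plan gives no figure to reproduce; the check applies the rules as written.

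**Worked example (illustrative dates).** First dose 22 May 2018; event recorded as resolved on 10 May 2018.

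| Start date as recorded | Imputed start | Class | Start after end? |
|---|---|---|---|
| wholly missing | 22 May | treatment-emergent | yes, by 12 days |
| 2018 only | 22 May | treatment-emergent | yes, by 12 days |
| May 2018 | 22 May | treatment-emergent | yes, by 12 days |
| April 2018 | 30 April | prior | no |

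**How often the rule converts such an event.** Inputs: screening of N days, with N from 7 to 21 (Protocol 12.1). Assumptions: first-dose dates spread evenly over a 365-day year, and equal weight on every start/end pair in which the event starts 1 to N days before dosing and ends before dosing.

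An event starting i days before dosing has i possible end dates, so the mean lag from start to first dose is Σi² / Σi = (2N + 1)/3 days. That is 15/3 = 5.0 for N = 7, 29/3 = 9.67 for N = 14, and 43/3 = 14.33 for N = 21.

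- *Day missing.* The event is converted if its start is in the first-dose month. For a lag of i days, 12i of the 365 first-dose dates put the start in an earlier month. The share converted is 1 − (12/365) × (2N + 1)/3:
  - N = 7: 1 − 60/365 = 83.6%
  - N = 14: 1 − 116/365 = 68.2%
  - N = 21: 1 − 172/365 = 52.9%
- *Year only.* Only a change of calendar year prevents conversion. The share is 1 − (1/365) × (2N + 1)/3, which gives 98.6%, 97.4% and 96.1%.
- *Wholly missing.* 100%, whatever the screening length.

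A full enumeration of first-dose dates and start/end pairs gives the same percentages. Every converted event has an imputed start after its recorded end.

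**Effect on a cohort.** Planned cohort sizes are 18, 14 and 14 (Protocol 7.1). One subject is 1/18 = 5.6% or 1/14 = 7.1%. SAP 8.3.1 defines the most common treatment-emergent events as those in at least 5% of subjects in any cohort, so one subject is enough to meet that threshold.

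**Related branches.** The rules that impute 31 December or the last day of an earlier month can also place a start after a recorded end date, but the event stays prior, so only the listing is inconsistent.

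**The case against.** The strongest reply is that this needs several things at once: an adverse event within a screening period of at most three weeks, an onset date that stays incomplete, and an end date complete enough to show resolution before Day 1. Protocol 10.3.1 asks the investigator for the onset date, and events are reviewed at screening and again at Visit 2, so recall is short. The analyses are descriptive by cohort, the stopping rules in Protocol 6.2 set no threshold on treatment-emergent events, and the error runs toward over-reporting harm. The event also remains in the listing of all adverse events (Listing 16.2.7.1), where a start after the resolution date could be noticed. All of this stands and limits the importance of the point. It does not correct the tables, and an imputation rule has to be right for the dates that queries leave unresolved.

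Three stronger readings are tempting and are not supported:

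- A reader might infer that the rule converts 64% to 87% of day-missing screening events. Those are the shares of *all* screening onsets that fall in the first-dose month: with onset uniform over N days the mean lag is (N + 1)/2, so 1 − (12/365) × 11 = 63.8% for 21 days and 1 − (12/365) × 4 = 86.8% for 7 days. They include events that continue past Day 1, for which the existing rule is defensible. They would apply to pre-dose-ended events only if the chance of having ended did not depend on how early the event began.
- A reader might infer that each such event adds 5.6 or 7.1 points. SAP 5.7 counts subjects, not events, so the step occurs only if the child is not already counted in that row.
- A reader might infer that the safety conclusions are materially distorted. The documents give no frequency of incomplete dates that would support this.

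**Conclusion.** The rule is wrong as written for one identifiable class of record: an adverse event with an incomplete start and a recorded end before Day 1. Conditional on such a record, conversion to treatment-emergent is certain or nearly so when the start month is unknown, and ranges from about half to more than four fifths when only the day is missing. The ranges rest on evenly spread first-dose dates and equal weight on start/end pairs; another distribution of event durations would move the day-missing figures. They are not expected frequencies. The step of 5.6 or 7.1 points is a ceiling at the planned cohort sizes. With descriptive analyses and a bias toward over-reporting, this is a minor correction, but it removes a logically impossible result.

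**What to change.** Add to the adverse event rules in SAP 8.1.1.1:

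> The imputed start date is the earlier of the date given by the rules above and the recorded end date. Where the end date is partial, the latest date it allows is used as the cap, for this comparison only.

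An event whose capped start falls before the first dose is then a prior event under the existing SAP 8.3.1 definition. If the end date is missing, or falls on or after the first dose, the cap does not alter an imputed first-dose date, so the conservative default is kept wherever timing is truly uncertain. In the worked example the start becomes 10 May in the first three rows, and the event is prior. The cap also removes the listing inconsistency in the last-day-of-month and 31 December branches.

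The cost is one SAP rule and one programming condition. The limit on the partial-date cap matters because the SAP otherwise leaves adverse event end dates unimputed. SAP 7 applies the same methods at the cohort-by-cohort interim analyses; if any has already been run, a resulting change in treatment-emergent counts should be noted in the SAP's change record and in the study report.

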8.1.1.2 Visit Window

Visit windows are defined for visit-specific parameters as following:

Table 2 Visit Window

Parameter	Study Period	Analysis Visit	Target Relative Day (s)*	Visit Window (Relative Days)*
HbA1c, Anti-insulin antibody	Screening	Screening	-21 to -7	[Day of ICF signed, - 1]
	Titration	Week 4 (Visit 15, EOT)	29	[22, 36]
	Extension	Month 12 (Visit 28, EOT)	Start day of the extension period + 365	[Start day of the extension period + 337, End day of the extension period + 393]
FEV ₁	Screening	Screening	-21 to -7	[Day of ICF signed, - 1]
	Titration	Day 1	1	No visit window, data collected on that day will be summarized by nominal time point
		Week 2 (Visit 9)	15	[8, 21]
		Week 4 (Visit 15, EOT)	29	[22, Treatment end day of the titration period]
		Follow-up	36	[Treatment end day of the titration period + 1, End day of the titration period]. Only subjects who opt not to participate in the extension period should have this visit.
	Extension	Month 3	Start day of the extension period + 91	[Start day of the extension period + 77, Start day of the extension period + 105]
		Month 6	Start day of the extension period + 183	[Start day of the extension period +169 , Start day of the extension period +197]
		Month 9	Start day of the extension	[Start day of the extension period +260, Start day of the extension period +288]

Parameter	Study Period	Analysis Visit	Target Relative Day (s)*	Visit Window (Relative Days)*
			period + 274	
		Month 12 (Visit 28, EOT)	Start day of the extension period + 365	[Start day of the extension period + 351 , Treatment end day of the extension period]
		Follow-up	Start day of the extension period + 396	[Treatment end day of the extension period +15, End day of the extension period]
Vital Signs and 7-Point SMBG	Screening	Screening	-21 to -7	[Day of ICF signed, - 1]
	Titration	Day 1	1 (for Vital Signs only)	No visit window, data collected on that day will be summarized by nominal time point
		Week 1 (Visit 5)	8	[5, 11]
		Week 2 (Visit 9)	15	[12, 18]
		Week 3 (visit 12)	22	[19, 25]
		Week 4 (Visit 15, EOT)	29	[26, Treatment end day of the titration period]
		Follow-up (for Vital Signs only)	36	[Treatment end day of the titration period +4, End day of the titration period]. Only subjects who opt not to participate in the extension period should have this visit.
	Extension	Month 3	Start day of the extension period + 91	[Start day of the extension period + 77, Start day of the extension period + 105]
		Month 6	Start day of the extension period + 183	[Start day of the extension period +169 , Start day of the extension period + 197]
		Month 9	Start day of the extension period + 274	[Start day of the extension period +260 , Start day of the extension period +288]

Parameter	Study Period	Analysis Visit	Target Relative Day (s)*	Visit Window (Relative Days)*
		Month 12 (Visit 28, EOT)	Start day of the extension period + 365	[Start day of the extension period +351 , Treatment end day of the extension period]
		Follow-up (for Vital Signs only)	Start day of the extension period + 396	[Treatment end day of the extension period + 15, End day of the extension period]

* Start/end day is calculated as the corresponding start/end date – Study Day 1 +1.

- Data will be assigned to analysis visits using the date of measurement and the visit windows (see [Table 2](#) above).
- If multiple measurements are collected within the same visit window, (1) for Screening visit, the last measurement will be used for analyses; (2) for post-baseline visits, the measurement that is closest to the target relative day will be used for analyses. In the event of a tie, the later measurement will be selected for analyses.
- In addition to the analysis visits listed in the table above, a visit of ‘Early Termination’ will also be included, for both the titration period and the extension period. For subjects with early discontinuation, data collected at the Early Termination visit will be summarized and presented at that visit, no matter whether the data has fallen into the visit window of any other visit or not (i.e., for example, if the value from Early Termination visit also falls into the visit window of Week 4, it will be summarized both with the Week 4 data, and with the other data collected at the Early Termination visit). By doing so, special attention can be drawn to the data collected at Early Termination, so if there is any particular safety data pattern associated with early discontinuation, it could be more easily recognized.
- Values which are not collected at Early Termination visits and do not fall into any of the visit windows will not be included in by-visit data summary, but will be presented in subject-listings
- If measurements are taken at multiple scheduled time points on the same day, data will be summarized based on nominal time points. Data collected at unscheduled time points will not be used for analyses.
- Visit specific parameters which are not included in [Table 2](#), e.g., urine cotinine tests and pregnancy tests, will not be summarized by visit and will only be presented in subject-listings.

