5.4 Study Period

Two study periods are defined: an approximately 4-week titration period (Visit 2 – Visit 16, including PK assessments at Day 1) followed by an optional 52-week extension period (Visit 17 – Visit 29). Participants in the titration period are defined as subjects who take at least one dose of study drug in the titration period and participants in the extension period are defined as subjects who complete the titration period and opt to participate in the extension study.

Start date of the titration period is defined as Study Day 1. For subjects who do not participate in the extension period, end date of the titration period is defined as the last visit/contact date; for

subjects who participate in the extension period, end date of the titration period is defined as the date of Visit 15.

Start and end date of the extension period are defined for subjects who participate in the extension period only. Start date is defined as date of Visit 15 +1 day, and end date is defined as the last visit/contact date.

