5.5 Study Drug Exposure

For each subject, information regarding study drug exposure will be derived from the eCRF and study drug dosing eDiary data. Here is a summary:

- First dose date is defined as the date the first study drug dose is taken, as shown in the eCRF ('AFREZZA[®] dosing' page at Visit 2).
- Last dose date is defined as the date the last study drug dose is taken, as shown in the eDiary.
- Period-specific treatment start date:
 - Treatment start date in the titration period is defined as Study Day 1.
 - Treatment start date in the extension period is defined for subjects who participate in the extension period only, as the date the first study drug dose is taken after the date of Visit 15.
- Period-specific treatment end date:
 - Treatment end date in the titration period is defined as:
 - The date the last study drug dose is taken, for subjects who do not participate in the extension period;
 - The date the last study drug dose is taken prior or on the date of Visit 15, for subjects who participate in the extension period
 - Treatment end date in the extension period is defined for subjects who participate in extension period only, as the date the last study drug dose is taken.
- Total Exposure time (days) is defined as last study dose date – first study dose date +1.
- Period-specific exposure time (days) is defined as period-specific treatment end date – period-specific treatment start date +1.
- Total daily dose is defined as the sum of all doses of AFREZZA[®] taken during a day.
- Prandial dose at a meal is defined as the sum of the pre-meal dose and the post-meal dose given at that meal. Per protocol, subjects should take a dose at beginning of each meal, and the post-meal dose will be given as needed to keep the blood glucose level in control.

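### The Week 4 (Visit 15) windows for FEV1 and vital signs close on the last eDiary dose date, so a completer whose last logged dose precedes Visit 15 has no Week 4 value

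*SAP*

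**What the plan says.** SAP Section 8.1.1.2 places each value in an analysis visit by its date and the windows in Table 2, not by the visit at which it was collected. If several post-baseline values share a window, the one nearest the target day is used. A value outside every window appears only in listings. The one exception is the Early Termination visit, which has its own row.

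For the titration period, Table 2 gives these windows:

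- FEV1, Week 4 (Visit 15, EOT), target Day 29: "22, Treatment end day of the titration period".
- FEV1, Follow-up, target Day 36: "Treatment end day of the titration period + 1, End day of the titration period".
- Vital signs, Week 4 (Visit 15, EOT), target Day 29: "26, Treatment end day of the titration period".
- Vital signs, Follow-up, target Day 36: "Treatment end day of the titration period +4, End day of the titration period".

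Both Follow-up rows add: "Only subjects who opt not to participate in the extension period should have this visit".

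SAP Section 5.5 defines the treatment end date for the titration period as "The date the last study drug dose is taken, for subjects who do not participate in the extension period"; for extension participants it is the last dose on or before Visit 15. The source is the diary: "Last dose date is defined as the date the last study drug dose is taken, as shown in the eDiary". SAP Section 5.4 adds that for "subjects who participate in the extension period, end date of the titration period is defined as the date of Visit 15".

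HbA1c and anti-insulin antibody, also collected at Visit 15, have a fixed Week 4 window of Day 22 to Day 36.

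**The concern.** The row is named for Visit 15, but its upper limit is a dosing date that need not equal the Visit 15 date. When the last logged dose is earlier, the visit lies outside its own row. Two measurements from the same visit can then be handled differently: the FEV1 moves to Follow-up, while the vital signs may leave the by-visit summary altogether.

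The outputs affected are the Week 4 rows of Table 14.3.4.1 (FEV1) and Table 14.3.3.1 (vital signs), both marked for the DMC in SAP Appendix 3. Whether a subject contributes would depend on whether a dose was logged on the visit day, not on whether the measurement was made. Table 14.3.4.2 (clinically relevant decline) may also be affected. That depends on how the eCRF indicator and the denominator of subjects attending the visit are programmed (SAP Section 8.3.5).

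**Working it through.** **Inputs.** Visit 15 is on Day 29 ± 1 and Visit 16 on Day 36 ± 3 (protocol Section 1.1). Titration spirometry is scheduled only at Visits 2, 9, 15 and 16 (SAP Section 8.3.5). Visit 12 vital signs (Day 22 ± 1) fall in the Week 3 window, Days 19 to 25. So only Visit 15 is scheduled to supply Week 4 for either measure.

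Let V be the day of Visit 15, L the day of the last logged dose, and g = V − L.

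**One case.** V = 29, L = 28, Visit 16 on Day 36.

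| | Week 4 window | Follow-up opens | Where Visit 15 lands |
|---|---|---|---|
| FEV1 | Days 22 to 28 | Day 29 | Follow-up; 7 days from target against 0 for Visit 16, so not used |
| Vital signs | Days 26 to 28 | Day 32 | No window |

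If Visit 16 is missed, the end-of-treatment FEV1 is reported as the Follow-up value.

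**General rule.**

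- Visit 15 is in Week 4 only if V ≤ L, that is g ≤ 0.
- For FEV1, any g ≥ 1 puts Visit 15 in Follow-up, which opens on L + 1.
- For vital signs, Follow-up opens on L + 4. Visit 15 is in no window for g = 1 to 3, and in Follow-up for g ≥ 4.
- In Follow-up, Visit 15 (Day 28 to 30) is 6 to 8 days from Day 36 and Visit 16 at most 3, so Visit 16 is always used.

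**Count over possible dates.** V = 28, 29 or 30; g = 0 to 6; Visit 16 on Day 33 to 39. That is 3 × 7 × 7 = 147 combinations.

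| | FEV1 | Vital signs |
|---|---|---|
| g = 0: both visits in the right row | 21 of 21 | 20 of 21 |
| g = 1 to 6: Week 4 empty | 126 of 126 | 126 of 126 |
| Proposed rule, all g: both visits in the right row | 147 of 147 | 147 of 147 |

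The single miss at g = 0 has the last dose and Visit 15 on Day 30 and Visit 16 on Day 33; vital-sign Follow-up then opens on Day 34. The 126 of 126 follows directly from the window definition and says nothing about frequency.

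**Other Visit 16 timings.** The protocol also counts Visit 16 from Visit 15 (Section 12.1.3.5) and from the last treatment (Section 12.1), each 1 week ± 3 days. With the first, the current rule is fully correct in 21 of 147 combinations and the proposed rule in 147 of 147, for both measures. With the second, and Visit 16 after Visit 15, the figures are 21 of 129 and 129 of 129.

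**Extension participants.** Their titration period ends on the Visit 15 date. Read literally, for g ≥ 1 the FEV1 Follow-up window (L + 1 to V) contains Visit 15, although Table 2 says these subjects should not have that row. If the row is withheld from them, the value is in no window. Week 4 is empty on either reading.

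**Early terminators.** With the last dose on Day 2 to 27 and the visit 0 to 6 days later (26 × 7 = 182 combinations), the proposed rule changes none.

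**The case against.** The trigger is narrow. One dose logged on the visit date is enough, AFREZZA is taken at every meal (protocol Section 12.1.3), and an overnight fast is specified only for Visit 2. Doses are entered in the eDiary daily (Section 9.2.8) and sites resolve diary discrepancies (Section 8.8). A subject who stops for good several days before Visit 15 may count as an early termination, which has its own row. Closing an end-of-treatment window at the last dose could also be a deliberate on-treatment choice, particularly as the windows were tightened in SAP revision 1.1.

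Most of this stands as a limit on frequency. The realistic cases are a one-day gap, a missing diary entry, or a temporary switch to injectable insulin (Section 8.7) that spans the visit. They are still possible. Site visits are in the morning (Section 12.1) and supplies are returned at Visit 15 (Section 12.1.3.4). A last dose on Day 28 is compatible with a completed 28-day titration and a Day 29 visit.

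The on-treatment reading does not fit a row named for Visit 15. Nor does it explain why vital signs taken 1 to 3 days after the last dose belong to no row.

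Three further points are fair. The g = 0 miss arises only under the flow chart's Visit 16 window; under the text of Sections 12.1 and 12.1.3.5, a Day 30 last dose and visit put Visit 16 on Day 34 at the earliest. The protocol's study design section describes no optional extension, and the SAP cites Amendment 2, so the extension branch matters only if those rows are kept. And the proposed rule moves the start of vital-sign Follow-up for every subject attending Visit 15, although no scheduled measurement between Visits 15 and 16 is displaced.

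**Conclusion.** The concern holds, and it is minor. As written, any completer whose last logged dose precedes Visit 15 has an empty Week 4 cell for FEV1 and vital signs, unless an additional measurement happens to fall inside the shortened window. The number of such subjects cannot be derived from the documents and may be small. One subject is 1/18 = 5.6% of the planned Cohort 1, or 1/14 = 7.1% of planned Cohort 2 or 3.

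The consequence is bounded. The analyses are descriptive, the spirometry and vital-sign listings also go to the DMC, and adverse-event capture of verified decline does not depend on the windows. HbA1c and anti-insulin antibody are unaffected.

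The conclusion assumes that Table 2 is programmed literally and that Section 5.5 supplies the treatment end day.

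**What to change.** In SAP Table 2, for subjects who attend Visit 15, define the closing day as the later of the treatment end day of the titration period and the Visit 15 day. Then set:

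- FEV1 Week 4: Day 22 to the closing day.
- Vital signs Week 4: Day 26 to the closing day.
- Follow-up for both: from the day after the closing day to the end of the titration period.

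Leave the present rule for subjects without Visit 15, whom the Early Termination row covers, and for 7-point SMBG, which would need its own line because it now shares the vital-sign row.

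If the extension rows are kept, the Month 12 windows for FEV1 and vital signs have the same form and should end on the later of the treatment end day and the Visit 28 day. The extension Follow-up start (treatment end + 15) can stay; the two would overlap only if Visit 28 came 15 or more days after the last logged dose.

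The cost is SAP wording and programming, with no new data. The trade-off is that a Visit 15 value taken some days after the last logged dose counts as Week 4. A footnote giving the number of such subjects would make that visible.
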